3.2.1.2 Study periods

The following are defined as study periods:

Screening	Prior to the time of first dose of Zilucoplan® (Arm A) or IV antibiotic (Arm B)
Primary Assessment Period	For Arm A, from the date/time of first dose of Zilucoplan® to the end date* of the Primary Assessment Period For Arm B, from the date/time of first dose of IV antibiotic to the end date* of the Primary Assessment Period
Planned Active Treatment Duration	For both arms the planned active treatment duration is from D1 up to D14 or hospital discharge, whichever is earlier.
D28 (minimal assessments carried out (6-point ordinal scale, (S)AE supplemental oxygen need (Y/N), concomitant medication)	28 days post randomization (by phone call, unless still hospitalised)
Follow-up	12-22 weeks post randomisation

* The end date of the primary assessment period for each participant will be 28 days post-randomisation

The end of the study is defined by the date of the Follow-up visit for the last participant to complete their Follow-up visit. In the event that participants are lost to follow-up, the study is not deemed to have ended until the last participant dosed has had the opportunity to complete their follow-up visit as scheduled.

3.2.1.3 Nominal Days

The pre-specified protocol nominal days are labelled as follows:

- Day -1
- D1
- D2

- D6
- D15
- D28
- Follow-up

The study protocol specifies that clinical and laboratory parameters be collected as frequently as possible, which would be daily. A window of +/- 1 relative day for each specified nominal day after D2 (+ 1 day for D2) will be allowed if a measurement was not collected on the specified relative day. The window for D28 is +/- 3 days. If a large proportion of data fall outside this window, then increasing the window to +/-2 days for nominal D6, nominal D15 and D28 will be considered.

An additional indicator variable will be derived, DISCHARGE DAY (Y/N), which will identify the relative day that the participants was discharged from hospital. If discharge is on or earlier than relative day 6, between relative day 7 and relative day 15 inclusive or between relative day 16 and relative day 28 inclusive, an additional row mapping the results of the discharge visit to nominal D6, or nominal D15 and nominal D28 respectively. For the primary endpoints a LOCF approach will be utilized for the participants who discharge i.e. if a participant discharges at Day 4 then that oxygenation measure will be mapped to Day 6, Day 15 and Day 28. The approach may be extended to secondary parameters. Data from participants who leave hospital for reasons other than clinical improvement will not be mapped to the nominal days as described above. Participants who die whilst in hospital are not considered as ‘discharged’. Separate indicator variables will be derived to indicate whether a participant has died on a specific relative day and if treatment was discontinued due to an adverse event.

The Nominal Day variable with the above labels will be derived from the relative days and allowable window for all collected endpoints. Since the ideal is to take measurements as frequently as possible, some measurements of some endpoints will not have a Nominal Day associated with them. When these values (without an associated Nominal Day) are to be summarized, graphed or analysed in statistical models, Relative Day will be used as either a continuous variable or categorical as defined in the respective sections. Nominal Day will only ever be used as a categorical variable.

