4.1. Primary End Points + Time Points

To measure the effectiveness of SC Zilucoplan® treatment on restoring lung homeostasis, the **primary endpoint** of this intervention is **measuring oxygenation** at predose day 6 and day 15 (or at discharge, whichever comes first) through assessment of the mean and/or median change from pretreatment (day 1) to post-treatment (day 6 and 15 or at discharge, whichever comes first) PaO₂/FiO₂ ratio, P(A-a)O₂ gradient and a/A pO₂ ratio, which can easily be performed in the setting of clinical observation of patients admitted to the COVID-19 ward or ICU COVID-19 unit. These measurements derived from an arterial blood gas sampling are taken when the patient is sitting upright and breathing room air. Since supplemental oxygen will be indispensable in some patients, the A-a gradient will be normalized against age and FiO₂ expected A-a gradient, according to validated formulas. If patients leave hospital between day 6 and day 15, that day of discharge will be taken as measurement point for primary endpoint instead of day 15. For patients on ECMO the PaO₂/FiO₂ ratio and Aa-gradient cannot be calculated as in this case the FiO₂ will be missing. Therefore, the last available value of PaO₂/FiO₂ ratio and Aa gradient prior to ECMO can be used at that timepoint.

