7.1.2. Withdrawal and replacement of subjects

Subjects are free to withdraw from participation in the study at any time upon request. If patient decides to leave hospital between day 6 and day 15, treatment with Zilucoplan® will be terminated, and day of discharge will be used to calculate the day 15 endpoint.

An investigator must discontinue or withdraw a subject from the study for the following reasons:

- allergic reactions (anaphylactic shock) to Zilucoplan® or antibiotic used for prophylaxis of meningococcal disease. Allergy to an antibiotic, should lead to a switch to another antibiotic so that patients receive prophylaxis against meningococcal disease for at least 14 days after the last dose of Zilucoplan®.
- Pregnancy
- Significant study intervention non-compliance
- If any clinical adverse event (AE), laboratory abnormality, or other medical condition or situation occurs such that continued participation in the study would not be in the best interest of the subject
- If the subject meets an exclusion criterion (either newly developed or not previously recognized) that precludes further study participation
- Cases included in the trial with a 'tentative' diagnosis of COVID-19 in which it is not possible to get a confident diagnosis by serology or other means later in the disease course, will be withdrawn from the study as soon as it is clear that SARS-CoV2 was not the cause of the clinical presentation.

In all cases, the reason why subjects are withdrawn must be recorded in detail in the eCRF and in the subject's medical records.

In all patients that have received Zilucoplan® as a study medication (group A patients), prophylaxis for meningococcal disease using either 3^d generation cephalosporin IV daily or oral ciprofloxacin daily (or appropriate alternative) should be continued for 14 days after the last Zilucoplan® dose, even if patient retracted from the study, or was withdrawn from the study by the investigator. In case reason for

withdrawal was allergy to an antibiotic, an alternative antibiotic for prophylaxis should be given until 14 days after the last Zilucoplan® dose.

The following actions must be taken if a subject fails to return to the clinic for a required study visit (visit at 12-22 weeks post-randomization):

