2.2.1 Efficacy endpoint(s)

2.2.1.1 Primary efficacy endpoint(s)

- Change from baseline in PaO₂/FiO₂ ratio to Day 6 and Day 15 (or at discharge, whichever comes first)
- Change from baseline in P(A-a)O₂ gradient to Day 6 and Day 15 (or at discharge, whichever comes first).
- Change from baseline in a/A pO₂ ratio to Day 6 and Day 15 (or at discharge, whichever comes first)

These endpoints are derived from variables obtained from arterial blood gas sampling.

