3.8 Changes to protocol-defined analyses

The analysis of the primary endpoint described in the protocol omitted to add that baseline*day would be included as a fixed effect in the Mixed Model Repeated Measures (MMRM) analysis. This is needed in order to account for the fact that values from days closer to baseline are likely to be more correlated than values at days further apart from baseline. This is important if we include D28 and long-term follow-up in some of our analyses.

The primary analyses will be using Nominal Day as the categorical time point, and not strict relative day. This is because whilst the ideal is to take measurements as frequently as possible, the protocol only specifies specific days, which are the primary days for comparing between treatment arms. Therefore, windowing has been incorporated into the derivation of Nominal Day to ensure data that may not have been collected on the specific day of interest, but are within the window, are used. Sensitivity analyses using Relative Day (continuous and/or categorical) will be carried out as described in the relevant sections.

An additional variable will be created to indicate day of discharge and where needed, the results on the day of discharge will be mapped to the appropriate nominal day (Section 3.2.1.3).. This is to match with the sentence in Section 7.1.2 where it describes how to treat data if the day of discharge is prior to D15.

The SAP will not be amended for any changes to planned analyses or any additional analyses that are made after database lock

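### SAP 3.2.1.3 withholds the discharge blood gas from the day-15 primary analysis unless the patient left through clinical improvement, a condition that protocol 4.1 and 7.1.2 do not set

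*SAP*

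**What the plan says.** Protocol 4.1, on the primary endpoint: "If patients leave hospital between day 6 and day 15, that day of discharge will be taken as measurement point for primary endpoint", in place of day 15. It sets no condition on why the patient left.

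Protocol 7.1.2, in the paragraph on voluntary withdrawal, begins "If patient decides to leave hospital between day 6 and day 15" and ends by saying that the "day of discharge will be used to calculate the day 15 endpoint".

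SAP 2.2.1.1 defines the endpoint in the same unconditional way: "Change from baseline in PaO₂/FiO₂ ratio to Day 6 and Day 15 (or at discharge, whichever comes first". SAP 2.3 applies the discharge alternative to day 6 as well as day 15.

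SAP 3.2.1.3 maps the discharge result to nominal D6 or D15 and, for the primary endpoints, carries it forward to later nominal days. It then restricts this: "Data from participants who leave hospital for reasons other than clinical improvement will not be mapped to the nominal days as described above".

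SAP 3.8, the section for changes from the protocol, says of the discharge mapping: "This is to match with the sentence in Section 7.1.2 where it describes how to treat data" when discharge falls before D15. The restriction is not listed there as a change.

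**The concern.** The patient who chooses to leave is the case that protocol 7.1.2 covers by name, and the SAP leaves that patient out unless he or she had improved. A reader of SAP 3.8 is told that the two documents agree where they do not.

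Two patients can leave on day 10, each with a blood gas. The one judged to have improved has a D15 value in the primary analysis; the other does not. Retention of a measured primary value therefore turns on a judgement related to outcome, made by people who know the treatment arm. The primary model assumes missing at random, and that assumption becomes doubtful for values set aside in this way. If such departures, or how poorly these patients are doing, differ by arm, the D15 treatment difference could be biased.

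**Working it through.** **1. The plan's own figure.** Inputs from protocol 11.1 and SAP 2.4: 54 and 27 patients, difference 0.25 × 320 = 80, SD 105, two-sided 5%, dropout under 10%.

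- SE = 105 × √(1/54 + 1/27) = 24.75, and 80/24.75 = 3.23. Power = Φ(3.23 − 1.96) = 0.898 (0.891 with a noncentral t).
- After 10% loss (48.6 and 24.3): 0.866 (t: 0.857).

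The stated power above 85% is reproduced. This point does not challenge it.

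**2. Which values are lost.** SAP 3.2.1.3 allows ±1 day, so D6 takes days 5–7 and D15 takes days 14–16. I read the restriction as switching off only the discharge mapping, not this window.

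| Day of gas on leaving | Left improved (SAP) | Left for another reason (SAP) | Protocol support for using it |
|---|---|---|---|
| 2–4 | D6, carried to D15 | neither | general discharge wording only |
| 5–6 | D6, carried to D15 | D6 only | general discharge wording (day 6 is the boundary) |
| 7 | D15 | at most D6, if no day-6 value exists | 4.1 and 7.1.2, for D15 |
| 8–13 | D15 | neither | 4.1 and 7.1.2, for D15 |
| 14–15 | D15 | D15, through the window | 4.1 and 7.1.2, for D15 |

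The clear conflict is therefore at D15, for departures on about days 8–13. If the window were widened to ±2 days, as the SAP allows, days 9–12 would still have no nominal day.

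**3. Whether another analysis recovers them.** The MMRM in SAP 8.1.2 uses only nominal D6 and D15. The LOCF sensitivity analysis in SAP 8.1.3 is for gaps not caused by discharge, and death is the only case it lists. SAP 3.8 promises relative-day sensitivity analyses, but SAP 8.1.3 describes none for the primary endpoints. No planned analysis clearly brings the values back.

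**4. Illustrative size.** Let f be the share of an arm whose D15 value is dropped and D the amount by which their change falls short of the others'. In a simple comparison of observed means, dropping them overstates that arm's mean by f × D, so

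bias in A − B = (fA − fB) × D.

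The documents give neither f nor D. Assumed values:

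| Difference in share | D = 50 mmHg | D = 100 mmHg |
|---|---|---|
| 0 | 0 | 0 |
| 5 points | 2.5 | 5 |
| 10 points | 5 | 10 |

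The largest entry is 10/80 = 12.5% of the target difference. The sign follows whichever arm loses more. The formula ignores what the model recovers from the D6 value.

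**5. Precision.** If total D15 loss, from all causes, reached 12%, power would be 0.858 (t: 0.849); at 15%, 0.846 (t: 0.836). Power falls below 85% between 10% and 12% loss by the t calculation, and between 13% and 15% by the normal approximation.

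**The case against.** The strongest reply is that few patients are affected and nothing shows that they do worse. This has force on several counts.

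- **The loss is partial.** The window keeps some values, and a patient who leaves after day 6 normally still contributes D6.
- **The specific protocol sentences are limited.** They cover departures between day 6 and day 15 and only the D15 endpoint. For earlier departures the conflict rests on the general discharge wording in protocol 4.1, SAP 2.2.1.1 and SAP 2.3.
- **Leaving for another reason is not the same as leaving unimproved.** The SAP's category includes personal choice and transfer. SAP 3.6.2 and 8.2 treat transfers separately, and protocol 7.2 expects high retention.
- **A gas may not exist.** Someone who walks out may not have had the scheduled arterial puncture.

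A reader might go further and infer that missing at random must fail, or that both arms' D15 means are inflated. The documents do not support either: the SAP conditions on the reason for leaving, not on the D15 value, and the model conditions on baseline and D6. A reader might also assume 20% departures in one arm and 5% in the other. But 20% is twice the total dropout of under 10% assumed in protocol 11.1.

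Two replies do not remove the conflict. That an early gas is not a day-15 value applies equally to improvers, whose early values are carried forward. And although the SAP was written from protocol version 3.0, its section 3.8 cites the 7.1.2 sentence, and the change log for versions 4.0 to 6.0 records no change to it.

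**Conclusion.** The point holds as an undeclared contradiction between the SAP and protocol 4.1 and 7.1.2. It is clearest for the D15 value of patients who leave on about days 8–13 for a reason other than improvement. For departures before day 6 the support is weaker: gases on days 2–4 are lost for both time points, and those on days 5–7 can count for D6 only.

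The handling makes missing at random doubtful; it does not prove it false. Bias in the treatment difference is possible if departure shares or shortfalls differ by arm. Its size and direction are unknown. The 2.5 to 10 mmHg range rests wholly on the assumed 5 to 10 point difference in shares and 50 to 100 mmHg shortfall, and is zero when both are equal across arms. Confidence is high in the contradiction and low in any particular bias.

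**What to change.** Replace the restricting sentence in SAP 3.2.1.3 with wording such as:

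*For participants who leave hospital other than by death or transfer to another hospital, the discharge-visit blood gas, where taken, is mapped to nominal D15, or to D6 and D15 if they leave on or before day 6, whatever the reason for leaving. Transfers are handled under Sections 3.6.2 and 8.2.*

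Keep the reason for leaving as a flag, run the improvement-only mapping as a sensitivity analysis, and correct the statement in SAP 3.8. If the sponsor prefers to keep the restriction, SAP 3.8 should declare and justify it as a departure from protocol 4.1 and 7.1.2.

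The cost is one SAP sentence, one correction, one flag and one extra run. No new procedure is needed, because a discharge blood gas is already scheduled. The downside is that a few early values from patients who left for other reasons will stand in for D15, as already happens for improvers.

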3.2.2 Definition of Baseline values

3.2.2.1 General baseline

In general, Baseline values for efficacy and safety endpoints will be determined from the last non-missing data value collected prior to the first dose of Zilucoplan®, unless otherwise noted for a specific type of data in Arm A. For Arm B, baseline values will be the first value taken on the designated Day 1 of study medication, defined as the day the participant first receives IV antibiotic. For endpoints which measurements are not taken on Day 1, Baseline will be the value taken at Screening.

Note that for the Nominal Day variable, identified baseline values (whether they were actually taken at Day -1/Screening or pre-dose D1) will be mapped to D1. If this value was taken at Day -

1 (Screening), there will be a missing value associated with the Day -1 (Screening) level in order not to duplicate results.

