9.2. Study specific interventions

This is a hospital based intervention trial, in which patients with COVID-19 will be treated for a maximum of 14 days with Zilucoplan®. Patients with COVID-19 infection and respiratory failure are severely ill, and will require multiple daily clinical exams, blood sampling, vital parameter measurements, blood oxygenation measurements, and chest X-rays and/or CT. These are all part of the clinical management plan of the patients, and data stored in the electronic patient file will be used as part of the assessment of efficacy and safety profile of Zilucoplan®

At screening, a blood sample will be taken, preferentially during routine blood sampling, to determine exclusion criteria (minimally includes Ferritin, LDH, haptoglobin, D-dimers, CRP, creatinine, triglycerides, fibrinogen, eosinophils, lymphocytes, neutrophils, haemoglobin, WBC count, platelets, bilirubin, ALT and AST, procalcitonin and bHCG (females)). A clinical exam and ECG to be performed at screening or day 1 before administration of study medication. Any form of chest CT scan within 48h before randomization (low dose, HRCT, or Angio CT scan) must document a presence of bilateral ground glass infiltrates or bilateral consolidation.

On day 1, prior to Zilucoplan® treatment in group A, and during the day in group B control patients, two tubes of blood serum (2 x 6 ml), one EDTA 6 ml tube, one 4 ml DNA EDTA tube, and two optional EDTA tubes (2 x 10 ml, optional) will be collected for measuring blood cytokine and chemokine levels, complement, and activation of immune cells. Additionally, one extra EDTA 6 ml tube will be collected from patients in the active group for pharmacokinetics (PK). In both groups, an arterial blood gas determination via arterial puncture will be taken in upright position, after minimal 3 minutes without supplemental oxygen. In case of inability to sit upright: same position should be used for all measurements of PaO₂. In ventilated patients or ECMO patients ABG can be obtained from invasive arterial line. In ventilated patients the FiO₂ can be directly derived from mechanical ventilation settings. The FiO₂ at moment of ABG is documented in the eCRF, except for patients on ECMO.. Scores to be assessed include 6-point ordinal scale, SOFA score and HScore. Both scores to be evaluated at time of first drug administration (Arm A and Arm B).

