2.4 Determination of sample size

The outcome(s) on which the sample size calculation is based upon, is the primary endpoint measurement of oxygenation, defined as ratio of PaO₂/FiO₂.

The target difference is the difference from baseline measured at the primary endpoint (at day 6 and day 15) between the control and the treated group. Given a sample size of 81 participants, 54 on Zilucoplan® and standard of care and 27 on standard of care there would be >85% power to show a significant difference from standard of care at the 2 sided 5% level if the true underlying treatment difference was an 80 point difference (25% of 320, being the mean at hospital admission) in the PaO₂/FiO₂ ratio. This assumes a standard deviation of 105 and a dropout rate of less than 10%.

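### SAP 3.2.2.1 selects baseline by different rules in the two arms, so an Arm B primary baseline may be taken after treatment has started; this can bias the primary comparison but need not

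*SAP*

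**What the plan says.** SAP 3.2.2.1 sets the Arm A baseline as "the last non-missing data value collected prior to the first dose of Zilucoplan". It then says "For Arm B, baseline values will be the first value taken on the designated Day 1 of study medication", meaning the day of the first IV antibiotic. Endpoints not measured on Day 1 fall back to Screening, with no distinction by arm.

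Several other places bear on the rule:

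- **SAP 8.1.1** says PaO2 and PaCO2 are recorded at Screening/Day -1, D1, D6 and D15. It leaves the time of the Arm B measurements open, with a preference for a constant time of day.
- **SAP 8.1.2** uses baseline in the change score, as a covariate and in an interaction with Nominal Day.
- **SAP 3.2.1.1 and 3.2.1.2** already define a first dose of study treatment for each arm: Zilucoplan in Arm A and IV antibiotic in Arm B.
- **SAP 3.2.2.2** admits a value up to 2 hours post-dose when no earlier one exists, for sensitivity analyses only.
- **SAP 4.3** takes the first value when a day has several.
- **SAP Table 8.1**, in the ferritin and CRP row, describes D1 as the last pre-dose value.
- **Protocol 4.1 and 5.1** treat baseline as pretreatment, without distinction by arm.

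**The concern.** The selection rule depends on the arm. Arm A looks back from the first dose and takes the latest value. Arm B looks forward from the start of Day 1 and takes the earliest value, whether or not treatment has begun. The trial is open-label. SAP 2.2.1.2 expects about 24 hours between randomisation and dosing, although SAP section 2 says dosing follows very soon. The interval in which a baseline can be taken after allocation is known may therefore not be trivial.

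If PaO2/FiO2 moves on average over those hours, the two arms' baselines would differ for a reason unrelated to the patients. Randomisation does not protect against that, and adjusting for baseline reduces the effect without removing it.

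The safeguard is also one-sided. A post-dose value in Arm A is confined to a sensitivity analysis, while a post-dose Day 1 value in Arm B can enter the primary analysis as an ordinary baseline.

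**Working it through.** **1. The plan's own figure.** Inputs from SAP 2.4: 54 and 27 participants, difference 80, SD 105, two-sided 5%, dropout below 10%, power above 85%.

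- SE = 105 × √(1/54 + 1/27) = 24.75. Power = Φ(80/24.75 − 1.96) = 89.8%.
- After 10% dropout (48.6 and 24.3): SE = 26.09. Power = Φ(80/26.09 − 1.96) = 86.6%.
- A noncentral-t check gives 89.1% and 85.7%.

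The stated power is reproduced.

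**2. Which blood gas each rule selects.** Dose here means the first dose as defined in SAP 3.2.1.1.

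| Blood gases available | Arm A | Arm B |
|---|---|---|
| Day -1 only | Day -1 | Screening value, if the fallback (worded by endpoint) is applied per participant |
| One, Day 1 pre-dose | that value | that value |
| Day -1 and one Day 1 pre-dose | Day 1 | Day 1 |
| Day -1 and Day 1 post-dose | Day -1 | Day 1 post-dose |
| Two on Day 1, both pre-dose | the last (3.2.2.1) or the first (4.3) | the first |
| Day 1 post-dose only | none in the primary analysis; alternate baseline if within 2 hours | Day 1 post-dose, in the primary analysis |

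The rules agree in the second and third rows and, on the natural reading, in the first. They diverge in the fourth and sixth. In the fifth they diverge only if 3.2.2.1 overrides 4.3.

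**3. From a baseline shift to bias.** Let *f* be the share of Arm B affected, *s* the mean shift in those participants, and *b* the slope of follow-up on baseline.

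Bias in the adjusted A − B difference = *f* × *s* × *b*. For an unadjusted change score, *b* = 1.

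The documents give none of the three. With an assumed *s* = 20 mmHg:

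| *b* | *f* = 0.5 | *f* = 1 |
|---|---|---|
| 0.3 | 0.5 × 20 × 0.3 = 3 | 6 |
| 0.5 | 0.5 × 20 × 0.5 = 5 | 10 |
| 0.7 | 0.5 × 20 × 0.7 = 7 | 14 |

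Simulation with 6,000 trials per setting gave 2.6, 4.9 and 7.4 for *f* = 0.5, and 6.3, 10.2 and 13.9 for *f* = 1. Against the 80-point target, 3 to 7 mmHg is 3/80 to 7/80, or about 4% to 9%. An upward shift in Arm B baselines would favour Zilucoplan; a downward shift would count against it.

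**4. Effect on the test**, at SE 24.75:

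| Net bias (mmHg) | Two-sided type I error | Power if against Zilucoplan | Power if in favour |
|---|---|---|---|
| 0 | 5.0% | 89.8% | 89.8% |
| 5 | 5.5% | 85.8% | 93.0% |
| 10 | 6.9% | 80.7% | 95.3% |

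These figures use SD 105. If the model's residual SD is smaller, the same bias is larger relative to the SE.

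**The case against.** Much of the case on the other side stands.

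- **Many participants are unaffected.** Protocol 7.3 waives a new Day 0/1 blood gas if one less than 24 hours before randomisation exists. With a single pre-dose gas both rules normally choose it, and the bias is zero.
- **Pre-dose intent is visible.** SAP 3.2.1.2 ends Screening at first dose in each arm, the paragraph after the baseline rule speaks of Screening or pre-dose D1 values, and Table 8.1 does the same for ferritin and CRP. This shows what was probably meant, but the operative Arm B sentence does not say it.
- **Antibiotic exposure is not peculiar to Arm B.** Arm A also receives a cephalosporin, and its baseline is anchored to Zilucoplan, so an Arm A baseline may also follow an antibiotic dose. Different anchor events are unavoidable. The avoidable asymmetry is first against last, and the missing pre-dose condition.

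A reader might infer from Protocol 9.2 ("prior to Zilucoplan® treatment in group A, and during the day in group B control patients") that the control blood gas may be drawn late on Day 1. That phrase governs the blood tubes. The blood gas has its own sentence covering both groups, and the schedules leave the D1 column blank for it. The link to the primary endpoint rests on SAP 8.1.1.

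A reader might also infer that the rules build a systematic shift into the primary change score. They do not. A shift needs both divergent selection and a mean trend in oxygenation over the hours concerned, and the documents establish neither.

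**Conclusion.** The inconsistency is real and should be corrected. As written, the SAP permits an Arm B primary baseline taken after randomisation and after the start of study treatment, treats a Day -1 value differently by arm in some cases, and can lead two programmers to different primary datasets. The consequence is a possible arm-dependent bias of unknown size and direction. The 3 to 7 mmHg range rests on three assumptions (half of Arm B affected, a 20 mmHg mean shift, slopes of 0.3 to 0.7) and is not evidence that a bias exists. The alternate-baseline analysis in SAP 8.1.3 covers participants with no pre-dose value and does not align the two rules. The sample size calculation is unaffected.

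**What to change.** Use one rule for both arms: baseline is the last non-missing value before the arm's first dose of study treatment as defined in SAP 3.2.1.1 and 3.2.1.2, with Screening/Day -1 values eligible. Use post-dose values in either arm only under the alternate-baseline sensitivity analysis of SAP 3.2.2.2. Word the Screening fallback per participant, and reconcile SAP 3.2.2.1, SAP 4.3 and the ferritin and CRP row of Table 8.1. Report by arm how many baselines are Day -1, Day 1 pre-dose and Day 1 post-dose.

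The first-dose anchor is preferable to a cut-off at randomisation. Protocol 9.2 has SOFA and the ordinal scale scored at first drug administration, and a randomisation cut-off would displace valid pre-dose Day 1 values.

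The common rule removes the difference in selection, although the anchor events still differ by arm. The cost is SAP wording and a programming rule, with no new data. The downside is that a few Arm B participants with only a post-dose Day 1 value would have no primary baseline. They would enter only the sensitivity analysis, and only if they fall within its 2-hour window.
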